Researcher Study Protocol

Official Title: The Effect of Mobile Software "Let's Move" Program Developed Based on Transtheoretical Model on Sedentary Life Behaviors of University Students

NCT ID: not yet assigned

Record Verification: 14.07.2022

SUMMARY and KEYWORDS:

Sedentary life means a physically inactive, sedentary life and is the fourth leading risk factor for global deaths. It is reported that 70% to 85% of young people between the ages of 15-24, who make up 15.6% of the population of our country, are sedentary. This rate does not meet the physical activity guidelines recommended by the World Health Organization for young people. Sedentary lifestyle causes physical, biological and mental problems, increases the prevalence of non-communicable diseases and negatively affects academic achievement. Integration of technology into human life in the health dimension; It aims to reduce the obstacles of individuals to change their unhealthy behaviors and to increase their motivation to gain healthy behaviors. The Transtheoretic Model (TTM) is an easy-to-use and proven effective model for changing the prevalence of activity. Schools are the most effective medium to reach young individuals. However, considering the density of the school population and the inadequacy of school health nurses in our country; New approach techniques and innovative strategies are needed to reduce costs and save time. Therefore, in the first stage of this twostage research, it was aimed to develop the TTM-based 'Hadi Move' mobile software program and to test the effect of the mobile software program developed in the second stage on changing the sedentary life behaviors of university students. The universe of this research consisted of 290 students studying at a foundation university in Istanbul. The sample was calculated using the G-power (3.1.9.4) program. By taking 10% more of the sample, 97 students in the experimental group and 97 students in the control group will be randomly assigned through the SPSS program. TTM-based "Let's Move" mobile software program developed for the experimental group will be applied for 12 weeks. The effectiveness of the program will be evaluated with pre-test, post-test and follow-up test, International Physical Activity Questionnaire, daily step count smart bracelet and sedentary lifestyle TTM Sedentary Life Scales (Stages of Change, Change Process Scale, Self-Efficacy and Decisional Balance Scale). At the end of the research, the effectiveness of the 'Hadi Move' mobile software program developed in this research in changing the sedentary life will be tested. In addition, it is aimed to increase the number of steps, decrease in sedentary behaviors and make an active lifestyle permanent. All initiatives developed for TTM sedentary life behavior change stages will be made into a book and the results of the experimental research will be published, contributing and providing evidence to the international literature.

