- The place and time of the research; The research was planned to be carried out between September 2021 and September 2023 with university students studying in Istanbul Beykent University Vocational School health program.
- 3. The universe of the research; The universe of the research consists of Anesthesia Program (n=57), Operating Room Services Program (n=64), Oral and Dental Health Program (n=89), Medical Imaging Techniques (n=27) and First and Emergency Aid Program at Istanbul

Beykent University Vocational School. (n=53) university freshman students studying in departments with a high number of students and meeting the criteria for inclusion in the research constituted N=290. Students who meet the inclusion criteria and volunteer to participate will be included.

4. Sample; The sample of the study was calculated with the G-power (3.1.9.4) program, means: difference between two independent means analysis. When the effect size was 0.5, type error $\alpha = 0.05$, power 1- $\beta = 0.95$, the sample size was found to be 176 (experimental group 88, control group 88). Considering the sample loss that may occur due to various reasons, it was decided to include 194 (experimental group 97, control group 97) more than 10% of the sample. The groups will be randomly assigned to the experimental control groups through the SPSS program.

5. Inclusion, Exclusion, and Exclusion Criteria

5.1.Inclusion criteria for the study;

- First year students studying in Istanbul Beykent University Vocational School health program between September 2021 and September 2023,
- ➤ 18-25 years old,
- Being in the inactive (category 1) and minimally active (category 2) categories according to the International Physical Activity Evaluation Questionnaire,
- Not included in any physical activity program,
- Do not have any physical (orthopedic, chronic diseases, etc.) and mental problems diagnosed by a doctor,
- Accepting the measurement of body weight, height, body fat and muscle ratio and calculation of BMI before starting the research, at the 12th week and at the 6th month after its completion,
- > Agreeing to use pedometer (pedometer),
- > Having an iPhone, iPod touch and android based smart phone,
- ➢ Have an active internet connection on their phone,
- Students who voluntarily agree to participate in the research will be formed.

5.2. Exclusion and Exclusion Criteria;

➢ Willingness to leave the research.

6. Data Collection Tools and Format

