Educational videos to be used in the mobile software program will be prepared in the form of animation. Opinions and suggestions of sports trainers/trainers, physiotherapists and physicians/psychiatrists were received on the contents of the "Let's Move" Program prepared by the researchers.

8. **Intervention Plan of the Research**

Students whose activity scores are inactive and minimally active according to the results of the International Physical Activity Survey (IPAQ) will be included in the study.

Program with an online satisfaction survey.

The "Let's Move" Program will be shared with the control group.

9. Independent, Dependent and Control Variables of the Study

- The independent variable of the study; Mobile Software "Let's Move" Program Developed Based on Transtheoretical Model
- Dependent variables of the study; Number of Steps per Day, Physical activity MET score categories, Transtheoretic Model sedentary life Stages of Change, SL-SES score, SL-DBS benefit perception score averages, SL-DBS harm perception score averages, Physical activity walking, moderate, severe and total MET score averages, Body Mass Index categories, fat and muscle ratio values.
- Control variables of the study; age, gender, socio-economic level, people who do sports in the family, weather conditions, environmental conditions (areas where sports can be done), previous sports status
- Limitation of the research; The inability to include students who do not have an active internet connection was accepted as a limitation of the study.

10. Analysis and evaluation of research data

The analysis of the data will be carried out on the computer with the SPSS (Statistical Package for Social Sciences) 21 package program. In the statistical analysis of the data, descriptive analyzes will be given as percentage, mean and frequency. Chi-square will be used to evaluate the homogeneity of the Experimental and Control groups, and the t test or Mann Whitney U test will be used in the analysis of the data in the experimental and control groups. One Way Anova or Kruskal Wallis analysis of variance will be applied when comparing three or more groups. Statistical significance level will be accepted as p<0.05.

11. Ethical Permissions

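### Section 10 compares the arms with an unadjusted t test or Mann-Whitney U test although pre-test values are collected; adjusting the continuous outcomes for baseline would gain precision at almost no cost.

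*Protocol*

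**What the plan says.** The Summary states that "97 students in the experimental group and 97 students in the control group will be randomly assigned through the SPSS program" and that "The effectiveness of the program will be evaluated with pre-test, post-test and follow-up test". Section 5.1 dates this for the body measurements: entry requires "Accepting the measurement of body weight, height, body fat and muscle ratio and calculation of BMI before starting the research, at the 12th week" and again six months after completion. The same section makes the activity questionnaire an entry criterion, since students qualify by "Being in the inactive (category 1) and minimally active (category 2) categories according to the International Physical Activity Evaluation Questionnaire".

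Section 9 lists the dependent variables. Several are continuous: daily steps, the self-efficacy and decisional balance scores, "Physical activity walking, moderate, severe and total MET score averages", and the fat and muscle ratios.

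For comparing the two arms, Section 10 says that "the t test or Mann Whitney U test will be used in the analysis of the data in the experimental and control groups". The other tests it names do not fill the gap. Chi-square is for checking that the groups are alike, and "One Way Anova or Kruskal Wallis analysis of variance will be applied when comparing three or more groups". Section 9 names control variables, but Section 10 uses none of them, and pre-test outcome values are not among them.

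Section 4 bases the sample size on a comparison of two independent means with effect size 0.5, alpha 0.05 and power 0.95.

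**The concern.** In a randomised trial a student's pre-test value usually explains part of the variation in the same measure later. A comparison that ignores it leaves that variation in the error term, so the interval for the between-arm difference is wider than the collected data allow. Bias is not at issue.

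The information is already being gathered. Every student has a MET score before entry, because the questionnaire decides eligibility. Fat and muscle ratios are measured before the start, and the TTM scales are part of the pre-test. Recruiting more students instead is limited, because the source population is 290.

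The point covers only the continuous outcomes. Stage of change, activity category and BMI class need other models.

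**Working it through.** **Inputs.** From Section 4: 88 per arm, d = 0.5 (so SD = 1), alpha 0.05, target power 0.95. Assumed, because the protocol gives no value: pre-test/outcome correlation r = 0.3, 0.5 and 0.7.

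**Reproducing the plan's figure.** Section 4 reports that "the sample size was found to be 176 (experimental group 88, control group 88". With the noncentral t distribution, 174 degrees of freedom and noncentrality 0.5 × √(88/2) = 3.317, 88 per arm gives power 0.951 one-sided and 0.910 two-sided. One-sided, 88 per arm is the smallest size that reaches 0.95, so 176 reproduces. Two-sided, 105 per arm (210 in total) would be needed. Section 4 does not state sidedness, so both are shown.

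**Effect of adjustment.** ANCOVA multiplies the variance of the between-arm difference by 1 − r² and uses one more degree of freedom (173 remain).

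- Variance cut = r².
- Equivalent unadjusted size per arm = 88/(1 − r²).
- 95% half-width = 1.974 × √(2/88) × √(1 − r²) = 0.298 × √(1 − r²) SD.
- Power: noncentrality 3.317/√(1 − r²).

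| | Unadjusted | r = 0.3 | r = 0.5 | r = 0.7 |
|---|---|---|---|---|
| Variance cut | – | 9% | 25% | 49% |
| Equivalent n per arm | 88 | 96.7 | 117.3 | 172.5 |
| Half-width (SD) | 0.298 | 0.284 | 0.258 | 0.212 |
| Power, one-sided | 0.951 | 0.9655 | 0.985 | 0.9986 |
| Power, two-sided | 0.910 | 0.933 | 0.968 | 0.996 |

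At r = 0.4 the two-sided power is 0.949, so a correlation of about that size brings a two-sided test back to the stated 0.95 at the planned size.

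**If change scores are compared.** The variance factor is 2(1 − r), and the half-widths are 0.352, 0.298 and 0.230 SD, wider than ANCOVA at each r. The variance saving from ANCOVA is then (1 − r)/2, or 35%, 25% and 15%. At r = 0.3 the change score is worse than ignoring baseline.

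**Simulation, normal outcome** (20,000 runs, two-sided, r = 0.3/0.5/0.7). The t test had power 0.910/0.911/0.906 and ANCOVA 0.930/0.967/0.996. ANCOVA type I error was 5.0%/4.8%/5.1%.

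**Simulation, skewed outcome** (lognormal, 4,000 runs, d and r on the log scale, two-sided). Mann-Whitney had power 0.897/0.893/0.887 and a rank-based ANCOVA 0.918/0.956/0.991, with type I error 5.4%/4.8%/4.9%. In a further check with about 30% zeros, as MET components may have, rank ANCOVA had about 0.92/0.94/0.99 against 0.89 for Mann-Whitney, with type I error of 4–5%.

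**Restricted entry.** If eligibility removes the top 10% to 30% of a normally distributed baseline, a correlation of 0.5 falls to between 0.44 and 0.38. This is illustrative; the share excluded is not given.

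**Cost if r = 0.** The critical t moves from 1.97369 to 1.97377, which costs about 0.002 percentage points of power. Estimating the slope adds about 1/(176 − 4) = 0.6% to the variance.

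**The case against.** The planned test is valid, it matches the method used for the sample size, and covariate adjustment is often left to an analysis plan, which may exist unseen. Section 10 is also brief and may not be meant as a full list. The first two points stand: this is lost efficiency and not an error of inference. The others carry less weight, because the protocol names the between-arm test itself.

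Section 10 does not say whether the tests apply to post-test values or to changes. If it means changes, the saving at r = 0.7 drops from 49% to 15% and the figure of about 173 per arm no longer applies. That limits the size of the gain but does not remove it.

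The correlation is unknown, and the gain is small at r = 0.3. MET scores make up four of the continuous outcomes, and restricted entry probably puts them near that end. This stands. It applies less to the fat and muscle ratios and the TTM scores, which are not entry criteria.

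MET components will contain zeros, so a plain log transform fails, and a rank ANCOVA gives no difference in MET-minutes. The first difficulty is met by the rank version; the second is a real limit on what can be reported.

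Finally, the experimental group also completes the questionnaires inside the app. That record exists in one arm only and cannot serve as the covariate. The pre-test forms sent online to all accepted participants (Section 6) can.

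**Conclusion.** The concern holds. Section 10 fixes an arm comparison that ignores pre-test values the trial already collects. Against a post-test-only comparison with 88 per arm, the gain ranges from modest (two-sided power up by about 2 percentage points at r = 0.3) to large (the equivalent of nearly doubling the sample at r = 0.7).

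The size rests on the assumed correlations, the design effect size of 0.5 and analysis of post-test values. The direction of the gain does not depend on sidedness, and it holds against change scores at each correlation examined. Validity is not affected, so this is a change that should be made and not a fault that undermines the trial.

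**What to change.** In Section 10, make the between-arm comparison of each continuous outcome, at post-test and at follow-up, an ANCOVA of the outcome on group and its own pre-test value. Report the adjusted difference with its 95% confidence interval. State that the covariate is the pre-test record collected in both arms, not the in-app entry.

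For skewed outcomes such as MET scores, name a rank-based or transformed ANCOVA in advance. The rank-based form copes with zeros; an estimate on the original scale would then have to be reported beside it. If no pre-test step count is recorded, leave the step comparison unadjusted. Categorical outcomes stay outside this change.

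The cost is one or two sentences in Section 10, one degree of freedom per model and slightly more analysis work. No extra students or measurements are needed.

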Appendix 1. Socio-demographic characteristics diagnostic form

Your name and last name...

Your age...

Your gender:

() Female

() Male

1) Work status

- 1. () Working
- 2. () Not working

2) How would you rate your family's economic situation?

- 1. () Very bad-bad
- 2. () Average
- 3. () Good-Very good

3) Are you satisfied with your weight?

- 1. () Yes
- 2. () No

4) Do you smoke?

- 1. () Yes
- 2. () No

5) Do you drink alcohol?

- 1. () Yes
- 2. () No

6) On average, how much time do you spend on the phone per day?

- 1. () 0-59 minutes
- 2. () 1-2 hours 59 minutes
- 3. () 3-4 hours 59 minutes
- 4. () More than 5 hours

7) On average, how much do you watch TV per day?

- 1. () 0-59 minutes
- 2. () 1-2 hours 59 minutes
- 3. () 3-4 hours 59 minutes
- 4. () More than 5 hours

8) On average, how much time do you spend in front of the computer per day?

- 1. () 0-59 minutes
- 2. () 1-2 hours 59 minutes
- 3. () 3-4 hours 59 minutes
- 4. (...) More than 5 hours

9)	I don't do physical activity because I don't find time for it	1. () Yes	2. () No
10)	I don't do physical activity because I don't feel the need to do	1. () Yes	2. () No
	them		
11)	I don't do physical activity because there is no suitable	1. () Yes	2. () No
	environment in my area where I live		
12)	I don't do physical activity because I'm afraid of getting hurt	1. () Yes	2. () No
13)	I do not do physical activity because I don't have the financial	1. () Yes	2. () No
	means for the sport I am interested in.		
14)	I don't engage in physical activity because I've have other plans	1. () Yes	2. () No
	for my free time		
15)	I don't do it because my family and friends don't do physical	1. () Yes	2. () No
	activity		
16)	I don't do it because I've been injured while doing physical	1. () Yes	2. () No
	activity before		
17)	I don't do it because I feel pressured to do physical activity	1. () Yes	2. () No
18)	I don't do it because I don't know the health benefits of physical	1. () Yes	2. () No
	activities		
19)	I don't do it because I don't have the motivation to do physical	1. () Yes	2. () No
	activity		
20)	What are your other reasons for not being physically active? W	rite	1

Appendix 2. International Physical Activity Questionnaire Short Form

We would like to know about the activities you do in your daily life. Below you will find questions about your physical activity in the last 7 days. Please answer all questions even if you do not consider yourself a very active person. Think about your housework and yard work, the activities you do at work, the things you do to get from one place to another, the activities you do in your free time such as exercise or sports.

Thin	k of any vigorous, strenuous activity you have done for 10 minutes or more in the last						
7 da	ys.						
1	How many days in the past week did you engage in an activity that required heavy						
	physical activity, such as heavy lifting, digging, aerobics, basketball, soccer, or fast						
	cycling?						
	○ days per week						
	\circ I did not do vigorous physical activity. (If you have ticked this option, proceed						
	to Question 3)						
2	How much time did you usually spend doing vigorous physical activity on one of						
	these days?						
	 I don't know / I'm not sure 						
	○minutes per day						
	 ○ hours per day 						
3	Think about moderate physical activities you've done in the past week. These are						
	activities that last 10 minutes or longer, require moderate physical exertion, and						
	cause shortness of breath somewhat more often than usual.						
	How many days in the last week did you do moderate physical activity, such as						
	carrying light loads, cycling at a normal speed, folk dances, dancing, bowling, or						
	tennis? (other than walking)?						
	○ days per week						
	\circ I did not do any moderate physical activity. (If you have ticked this option,						
	proceed to Question 5)						
4	How much time did you usually spend doing moderate physical activity on one of						
	these days?						
	 I don't know/I'm not sure 						
	o minutes per day						
	○ hours per day						
5	Think about the time you spent walking in the past week. This could be walking at						
	work, at home, to get around, or just for recreation, exercise, or as a hobby.						
	In the past 7 days, how many days have you walked for at least 10 minutes at a						
	time?						

udes				
the time you spent at work, at home, working, or resting. This also includes the time				
you spent sitting at your desk, visiting a friend, reading, sitting, or watching TV while				
Ī				

Scoring and Scoring of the IPAQ Survey

Short form (7 questions); provides information on time spent walking, moderate and vigorous activities, and time spent sitting. Calculation of the total score of the short form includes the sum of the duration (minutes) and frequency (days) of walking, moderate-intensity activity, and vigorous activity. The energy required for activities is calculated with the MET-minute score. Standard MET values have been established for these activities. By using these values, daily and weekly physical activity level is calculated. These;

Physical Activities	MET value	Weekly MET score calculation
	(min.)	(min*day)
Vigorous Physical Activity	8.0 METs	Vigorous MET-min/week = 8.0 x
(questions 1 and 2)		minutes of vigorous activity x number of
		days of vigorous activity
Moderate-Intensity	4.0 MET	Moderate-intensity MET-min/week =
Physical Activity (questions		4.0 x minutes of moderate-intensity
3 and 4)		activity x number of days of moderate-
		intensity activity

Walking	(5th	and	6th	3.3 MET	Walkin	Walking MET-min/week = 3.3 x walking				
questions)					minutes x number of walking days					
Total wee	klv ME	T scor	e		Total	MET-min/week=	walking	+		
					moderate + severe (MET-min/week)					

For example; The walking MET-min/week score of a person walking for 3 days and 30 minutes is calculated as 3.3 X 3 X 30 = 297 MET-min/week.

Physical activity categories according to total MET scores according to IPAQ;

- ✓ Inactive Level; 599 MET and below
- ✓ Minimal Level; Between 600 MET-3000 MET
- ✓ Very Active Level; 3001 MET and above

7. Evaluation of the Problem; The IPAQ residency question is an additional determinant. It is not part of the scoring of physical activity

TTM Sedentary Life Stages Of Change Scale (SL-SCS);

Sedentary behaviors; It is defined as sitting, leaning, or physical activities that burn less than 1.5 METs of energy other than rest time and sleep. For example: sitting, studying, watching TV, playing video games and using a computer, etc. Some people go for a walk or do stretching exercises to reduce their sedentary time. they do.

Consider your long-term sedentary behavior while answering the questions below. Please be sure to read the questions carefully and choose the one that best describes your opinion from the 5 sentences below while answering the questions.

1) Can	1) Can you do enough physical activity almost every day?				
Yes ()		No ()			
2) Do you think you spend most of your day inactive?					
1.()	Yes, and I don't plan to give up my	sedentary lifestyle (sitting all the time, etc.)			
	these days. (Not Thinking Phase)				
2. ()	Yes, but I plan to give up a sedenta	ary lifestyle (sitting all the time, etc.) in the			
	next 6 months. (Thinking Phase)				
3. ()	Yes, but within the next 30 days, I pla	an to give up a sedentary lifestyle or reduce			
	these behaviors by doing small exercises from time to time. (Preparation				
	Phase)				
4.()	No, I am not inactive. In the last 6 m	onths, I gave up my sedentary lifestyle and			
	started doing physical activity freque	ently. (Movement Phase)			
5. ()	No, I am not inactive. I gave up the	sedentary lifestyle for more than 6 months			
	and started doing frequent and regu	lar physical activity. (Continuation Phase)			

TT	TTM Sedentary Life Self-Efficacy Scale (SL-SES)					
Self Som wou the ansv	F-Efficacy Scale The situations where people are sedentary are listed below. We Id like to know how much you can avoid sedentary behavior in following situations. Tick the appropriate number for your wer for each situation.	I don't trust at all	l trust a little	l am moderately confident	I trust so much	l am extremely confident
1.	I tell myself that I will not be inactive while doing my schoolwork.	1	2	3	4	5
2.	When I feel tired, I tell myself that I will not stay still.	1	2	3	4	5
3.	While playing a video game, using a computer, or watching TV, I tell myself that I will not stay still	1	2	3	4	5
4.	When I spend time with my friends or family who want to sit, I tell myself that I will not stay still	1	2	3	4	5
5.	When I'm on vacation or in my spare time, I tell myself that I won't be sedentary	1	2	3	4	5
6.	When I feel lazy, I to myself that I will not stay still.	1	2	3	4	5

Self-efficacy Scale; It is an individual's belief about himself/herself that he/she can successfully perform a certain behavior, and it reflects self-confidence. The scale consists of 6 items that include self-confidence in quitting sedentary behavior. It is a five-point Likert type. It ranges from 1: Not at all trusting to 5: Very confident. The minimum score to be taken from these scales will be '6' and the maximum score will be '30'. A high score on the self-efficacy scale indicates that the student's self-efficacy in changing sedentary life behavior has increased.

